3.2 Subject disposition

The number and percentage of subjects who completed study treatment or prematurely discontinued from the study treatment will be summarized with reasons for premature discontinuation. The reasons for study treatment discontinuation are as follows:

1. Adverse events
2. Lost to follow-up
3. Death
4. Disease progression
 - a. Radiological assessment
 - b. Clinical assessment
5. Protocol deviation
6. Non-compliance with study treatment
7. Pregnancy
8. Physician's decision
9. Subject/guardian decision
10. Study terminated by sponsor

In addition, the number and percentage of subjects who consent to be followed for survival will be presented.

For subjects who were screened but did not take the study treatment, a listing with reasons for screen failure will be provided. The reasons collected for screen failure are as follows:

1. Unacceptable past medical history/concomitant diagnosis
2. Intercurrent medical event
3. Unacceptable laboratory value(s)
4. Unacceptable test procedure result(s)
5. Did not meet diagnostic/severity criteria
6. Unacceptable use of excluded medications/therapies
7. Subject withdrew consent
8. Unknown
9. Other

In addition, a listing of subjects' deviations/violations during the study will be provided.

3.3 Study Treatment and other concomitant medications

Subjects receive ceritinib at 750 mg once daily. A complete treatment cycle is 28 days. There is no break between dosing cycles. For subjects who are unable to tolerate the protocol-specified dosing schedule, dose adjustments are permitted in order to allow these subjects to continue study treatment. Protocol section 6.3 provides the details.

In general, concomitant medications and therapies deemed necessary for the care of the subject are permitted (see Protocol Section 6.4.1 and 6.4.2), except as specifically prohibited

(see Protocol Section 6.4.3). All medications, procedures and significant non-drug therapies (including physical therapy, oxygen and blood transfusions) administered within 30 days prior to the administration of ceritinib and through 30 days after the last dose of study treatment will be recorded in the corresponding CRF page.

Detailed summaries of study treatment and other concomitant medications are described in Section 5 below.

4 Patient demographics and other baseline characteristics

Demographic data, medical history, disease characteristics and other baseline characteristics are collected at the screening visit.

In general, the baseline value will be considered as the last measurement observed prior to the first dose of study treatment, and includes assessments taken on the date of the first dose of study treatment.

Unless specified otherwise, for continuous data, the mean, standard deviation, median, 25th and 75th percentiles, minimum, and maximum will be presented. For categorical data, frequencies and percentages will be presented.

Demographic characteristics

Demographic variables include:

- Age (years), age group (<65, ≥65-<75, ≥75 years)
- Sex (Male, Female – able to bear children, premenarche, post menopausal, sterile of child bearing age)
- Race (Caucasian, Black, Asian, Native American, Pacific Islander, Other)

Medical history

Number and percentage of subjects with relevant and/or current medical history/conditions will be summarized by categories of conditions. For ongoing conditions, grade of condition (i.e., 1-4) will also be summarized. Medical history/current medical conditions will be coded using Medical Dictionary for Regulatory Activities (MedDRA). The MedDRA version used for reporting the study will be specified as a footnote in the tables/listings.

Disease characteristics

Disease characteristics variables include:

- Gene mutations as detected by local and central labs in pre-defined per-protocol mutation categories
- Primary tumor type (**Sponsor adjudicated**)
Note: The tumor type adjudication is made based on the combination of the primary site of tumor with the tumor histology/cytology as collected in the CRFs.
- Time (in months) from initial diagnosis to the first dose of ceritinib

- Time (in months) from date of most recent recurrence/relapse to the first dose of ceritinib
- Stage at initial diagnosis
- Age of biopsy samples (in months) calculated from date of biopsy sample date to the first dose of ceritinib

Other baseline assessments

- Vital signs (height, weight, body temperature, respiratory rate, sitting pulse, sitting systolic/diastolic blood pressures [SBP/DBP])
- 12 lead ECG (QTcF, heart rate, PR duration, QT duration, QRS duration)
- Cardiac imaging (LVEF)
- ECOG performance status
- Prior lines of antineoplastic medication therapy
- Prior antineoplastic radiotherapy (yes/no)
- Prior antineoplastic surgery (yes/no)

5 Study treatment exposure and other medications

5.1 Study treatment

Duration of ceritinib treatment (in months) and actual total dose (sum of daily ceritinib treatment) will be summarized with mean, standard deviation, median, 25th percentile, 75th percentile, minimum and maximum. Duration of the treatment is defined as the last dose date of ceritinib minus the first dose date of ceritinib + 1. The number and percentage of subjects with ceritinib exposure for the following categories will be presented as well: day 1 – day 61 (\leq 2 month), day 62 – day 122 ($>$ 2 months - \leq 4 months), day 123 – day 183 ($>$ 4 months - \leq 6 months), day 184 – day 244 ($>$ 6 months - \leq 8 months), day 245 – day 365 ($>$ 8 months - \leq 12 months), and \geq day 366 ($>$ 12 months).

Actual dose intensity and relative dose intensity of ceritinib will be summarized. Dose intensity is defined as the total dose of ceritinib (mg) divided by duration of ceritinib (in days). Relative dose intensity (in percent) is the actual dose intensity divided by planned dose intensity (i.e., 750 mg/day), and expressed in percent.

In addition, the number and percentage of subjects who had a dose change will be summarized with reasons for the change (as per protocol: AE, dosing error, lab test abnormality, scheduling conflict, or dispensing error).

5.2 Prior and concomitant medications/non-drug therapies

Prior and concomitant medications will be coded according to the World Health Organization-Drug Dictionary (WHO-DD). The WHO-DD version will be specified as a footnote in the tables/listings. Prior and concomitant medications are mutually exclusive, as defined below:

- Prior medications are defined as any medications with an end date prior to the first dose of ceritinib;
- Concomitant medications are defined as any medications taken during the treatment period (from the first dose date and on). Prior medications that are ‘ongoing’ at the time of first study treatment or whose end date is after first study treatment will be considered concomitant medication.

The number and percentage of subjects with prior medications, concomitant medications that started prior to ceritinib initiation, as well as concomitant medications that started after ceritinib initiation, will be summarized by preferred term. Non-drug therapies (surgical and medical procedures) will be listed for each subject. A standard imputation method will be used for partial start/stop date of medications.

6 Efficacy and PRO evaluation

6.1 Clinical Benefit Rate (CBR)

Clinical benefit is determined by investigator assessment for each tumor assessment and is defined as responses of CR or PR or SD \geq 16 weeks. In addition to tumor-specific measurements (e.g., radiological assessment of tumor response for solid tumors), progressive disease will also be considered when it was indicated either as a reason based on clinical assessment for the study treatment discontinuation or as a cause of on-treatment death. CR and PR (for solid tumors) require a confirmation that is at least a minimum of 4 weeks after the initial observation of response. Subjects who had a confirmed CR/PR or SD prior to 16 weeks, but discontinued prior to 16 weeks for reasons other than progressive disease, will have their clinical benefit defined as non-evaluable; subjects who had a confirmed CR/PR or SD prior to 16 weeks, but progressed prior to 16 weeks, will be considered as not achieving clinical benefit; subjects who had CR/PR/SD occurred prior to 16 weeks, but progressed at or after 16 weeks without evidence of CR/PR/SD at or after 16 weeks, will also be considered as not achieving clinical benefit. CBR will be analyzed by comparing achieved CBR with a historical control rate of each tumor type, and if there is at least 90% probability that the response rate in a tumor type exceeds the historical rate, then the tumor type will be considered a success; it will be considered as promising if the probability is between 80% and 90%. Details for the analyses of CBR are located in Section 10.

6.2 Overall Response Rate (ORR)

Overall response is determined by investigator assessment for each tumor assessment in the study. For subjects with solid tumors (other than lymphoma) the assessment criteria will be RECIST 1.1 and will include responses of CR and/or PR; for lymphoma, Cheson criteria will be used; for hematologic tumors, other appropriate hematological response criteria will apply. The number and percentage of subjects for different categories of overall response (e.g., for solid tumors – CR, PR, SD, PD, Not Evaluable) will be provided for solid tumors (non-lymphoma), lymphoma (if applicable), and each hematological tumor type (if applicable). Ninety-five percent (95%) exact confidence intervals (CIs) will be provided for the response rate(s) (e.g., for solid tumors – CR and/or PR) as well. For cohorts with at least 10 subjects,

overall responses will be summarized separately. Components of tumor assessments (e.g., for solid tumors – target lesion response, non-target lesion response, new lesion [yes/no]) will also be listed. In addition, Cancer Antigen-125 (CA-125) (if applicable) in the assessment of ovarian cancer response, Prostate-specific Antigen (PSA) (if applicable) in the assessment of prostate cancer will be listed.

The above analyses will be performed for the FAS.

6.3 Progression Free Survival (PFS)

PFS is defined as the time from the date of first dose of ceritinib to the date of the first documented disease progression/relapse or death due to any cause within 30 days of the last dose, and is calculated as $PFS = (\text{date of progression/relapse or death} - \text{date of first study treatment} + 1)$. Disease progression noted as the reason for discontinuation of treatment will be considered as a progression, thus will be considered as an event for PFS.

Subjects who discontinue or complete study treatment without disease progression will be censored at last adequate tumor assessment on or before the discontinuation/completion of the study. If there is no tumor assessment for the subject, the PFS will be censored at Day 1.

PFS will be summarized and graphed using the Kaplan-Meier product-limit method¹. The estimated median survival time, the corresponding 95% CIs², and 25th and 75th percentiles will be provided. In addition, survival rate estimates at 1, 2, 3, 4, 5, 6, and 12 months with 95% CIs will also be provided. For cohorts with at least 10 subjects, separate PFS analyses will be conducted for each cohort.

The above analyses will be performed for the FAS.

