10.5.2 Other secondary efficacy objectives

The secondary objectives of the study:

- To assess progression free survival (PFS) based on local investigator assessment per RECIST 1.1 or other appropriate hematological response criteria
- To assess overall survival
- To assess duration of response (DOR) based on local investigator assessment per RECIST 1.1 or other appropriate hematological response criteria
- To assess safety and tolerability

The secondary efficacy variable progression free survival (PFS) is defined as the time from the date of first dose to the date of first documented disease progression or relapse or death due to any cause.

PFS will be summarized and graphed using the Kaplan-Meier product-limit method for the entire study cohort. For cohorts with at least 10 subjects, separate PFS analyses will be conducted for each cohort. Patients who drop-out without progression will be censored at the time of last adequate assessment. The estimates of the 25th, median, 75th percentiles of the PFS and their 95% confidence intervals will be provided, if applicable.

Overall survival (OS) is defined as the time from the date of first dose to the date of death due to any cause. If a patient is not known to have died, survival time will be censored at the date of the last contact.

OS will be summarized and graphed using the product-limit method as above.

The duration of response applies only to patients whose best response was PR or CR. For patients with solid tumors the assessment criteria will be RECIST 1.1 and will include responses of CR and/or PR. For hematologic tumors other appropriate hematological response criteria will apply and are included in the appendices. The duration of response is defined as the time from the first documented response to the date first documented disease progression or relapse or death due to any cause. The duration of response will be summarized descriptively for the entire study cohort.

If the study primary efficacy endpoint is not met, Novartis may decide not to conduct some of the above secondary efficacy analyses but instead provide those endpoints in listings only.

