PD ⁵	Increase of > 25% from lowest response value in any one or more of the following: Serum M-component and/or (the absolute increase must be > 0.5 g/dL) ⁶ Urine M-component and/or (the absolute increase must be > 200 mg/24 h) Only in patients without measurable serum and urine M-protein levels; the difference between involved and uninvolved FLC levels. The absolute increase must be > 10 mg/dL Bone marrow plasma cell percentage; the absolute percentage must be > 10% ⁷ Definite development of new bone lesions or soft tissue plasmacytomas or definite increase in the size of existing bone lesions or soft tissue plasmacytomas Development of hypercalcaemia (corrected serum calcium > 11.5 mg/dL or 2.65 mmol/L) that can be attributed solely to the plasma cell proliferative disorder
Relapse	Clinical relapse requires one or more of: Direct indicators of increasing disease and/or end organ dysfunction (CRAB features). ⁶ It is not used in calculation of time to progression or progression-free survival but is listed here as something that can be reported optionally or for use in clinical practice Development of new soft tissue plasmacytomas or bone lesions Definite increase in the size of existing plasmacytomas or bone lesions. A definite increase is defined as a 50% (and at least 1 cm) increase as measured serially by the sum of the products of the cross-diameters of the measurable lesion Hypercalcemia (> 11.5 mg/dL) [2.65 mmol/L] Decrease in haemoglobin of > 2 g/dL [1.25 mmol/L] Rise in serum creatinine by 2 mg/dL or more [177 mmol/L or more]

Response IMWG Criteria¹ BGM Durie et al. International uniform response criteria for multiple myeloma. Leukemia (2006) 1-7.² Adapted from Durie BGM, et al. Leukemia 2006; 20: 1467-1473; and Kyle RA, Rajkumar SV. Leukemia 2008;23:3-9

Note: A clarification to IMWG criteria for coding CR and VGPR in patients in whom the only measurable disease is by serum FLC levels: CR in such patients is defined as a normal FLC ratio of 0.26–1.65 in addition to CR criteria listed above. VGPR in such patients is defined as a >90% decrease in the difference between involved and unininvolved free light chain (FLC) levels.

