³ Confirmation with repeat bone marrow biopsy not needed.⁴ Presence/absence of clonal cells is based upon the kappa/lambda ratio. An abnormal kappa/lambda ratio by immunohistochemistry and/or immunofluorescence requires a minimum of 100 plasma cells for analysis. An abnormal ratio reflecting presence of an abnormal clone is kappa/lambda of > 4:1 or < 1:2.⁵ All relapse categories require two consecutive assessments made at any time before classification as relapse or disease progression and/or the institution of any new therapy. In the IMWG criteria, CR patients must also meet the criteria for progressive disease shown here to be classified as progressive disease for the purposes of calculating time to progression and progression-free survival. The definitions of relapse, clinical relapse and relapse from CR are not to be used in calculation of time to progression or progression-free survival.⁶ For progressive disease, serum M-component increases of >1 gm/dL are sufficient to define relapse if starting M-component is >5 g/dL.⁷ Relapse from CR has the 5% cut-off versus 10% for other categories of relapse.⁸ For purposes of calculating time to progression and progression-free survival, CR patients should also be evaluated using criteria listed above for progressive disease.

14.15 Appendix O: Myeloproliferative Neoplasm (MPN) Symptom Assessment Form Total Symptom Score (MPN-SAF TSS)

Name: _____ Date: _____

Fill out the form below to track the burden of your symptoms.

For each symptom, please **circle the number** that best describes how severe that symptom is, on a scale of 0 to 10, with **0 being absent or as good as it can be** and **10 being worst imaginable**. Make sure you circle a number for every symptom. Be sure to **share your answers** with your haematologist or other healthcare professional.

Symptom - 1 to 10, 0 if absent and 10 being worst imaginable

Please rate your fatigue (weariness, tiredness) by circling the one number that best describes your WORST level of fatigue during the past **24 hours**

Fatigue	0	1	2	3	4	5	6	7	8	9	10
(ABSENT)	(WORST IMAGINABLE)										

Circle the one number that describes how much difficulty you have had with each of the following symptoms during the **past week**

Filling up quickly when you eat (early satiety)	0	1	2	3	4	5	6	7	8	9	10
(ABSENT)	(WORST IMAGINABLE)										

Abdominal discomfort	0	1	2	3	4	5	6	7	8	9	10
(ABSENT)	(WORST IMAGINABLE)										

Inactivity											
0	1	2	3	4	5	6	7	8	9	10	

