2.1 Change in planned analyses from the protocol

The protocol specifies that analyses are to be conducted by "patient group" which is formed by the types of cancer at study entry. That is, subjects with the same tumor type will be considered as in the same "patient group". For efficacy analyses, with exception of the primary analysis of clinical benefit rate (i.e., summarized by 'patient group'), other descriptive summaries in general will be produced overall for all ceritinib-treated subjects. Separate summaries may be produced for those groups with at least 10 subjects. All subjects will be combined for any safety analyses.

[figure not shown]
In the event of a low response rate, DOR will only be listed, and not tabulated. Subjects who had no disease progression/death will be censored at last adequate tumor assessment on or before the discontinuation/completion of the study.

For determination of PFS events, due to tumor assessments post study treatment are not collected, deaths occurred more than 30 days post treatment without prior progressive disease/relapse of disease will not be considered as an event.

For overall survival analysis, no KM method will be used due to early study termination. Descriptive summaries will be provided instead.

For vital signs, values will be descriptively summarized by nominal visit. Separate summaries of significant abnormalities will not be provided, but will be reflected in adverse events (AEs).

For cardiac imaging, due to data collection is only as clinically indicated, thus only listing will be provided.

3 Subjects and treatments

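### The SAP counts documented relapse as a PFS event in every disease, although Appendix N bars relapse from PFS in multiple myeloma (minor)

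*SAP*

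**What the plan says.** SAP 6.3 starts the PFS clock when ceritinib is begun and stops it at "the date of the first documented disease progression/relapse or death due to any cause". It counts a death only if it falls no later than 30 days after dosing ends, and its formula repeats the pairing of progression with relapse. SAP 2.1 does the same when it says that deaths more than 30 days after treatment "without prior progressive disease/relapse of disease will not be considered as an event".

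Protocol 10.5.2 runs PFS from first dose "to the date of first documented disease progression or relapse or death due to any cause". The objective listed in the same section is "To assess progression free survival (PFS) based on local investigator assessment per RECIST 1.1 or other appropriate hematological response criteria".

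Protocol 5.2, item 8c, admits patients with symptomatic multiple myeloma, and 7.2.1.3 has their response scored by the IMWG criteria in Appendix N. On clinical relapse, the relapse row of that appendix says: "It is not used in calculation of time to progression or progression-free survival". Footnote 5 is broader: "The definitions of relapse, clinical relapse and relapse from CR are not to be used in calculation of time to progression or progression-free survival". Footnotes 5 and 8 add that patients in CR are to be judged by the progressive disease criteria for these endpoints.

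**The concern.** One set of documents gives two PFS rules for the same patient. The SAP and protocol 10.5.2 make relapse an event everywhere. The response criteria that the protocol adopts for myeloma say it is not one.

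This matters only if relapse can be recorded when progressive disease is absent. If it can, the literal SAP rule dates the event too early, or creates an event where Appendix N would leave the patient at risk or censored. Two programmers working from the same documents could derive different PFS times for one patient.

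**Working it through.** No sample size, power or event figure is at issue, so the check is a comparison of texts.

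**Step 1: does any section except myeloma?** SAP 6.3, SAP 2.1 and protocol 10.5.2 each name relapse beside progression. None mentions myeloma or Appendix N in defining the event.

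**Step 2: does Appendix N apply?** Yes. Eligibility (5.2, item 8c), assessment (7.2.1.3) and the visit schedule (Table 7-1) all provide for myeloma.

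**Step 3: can relapse occur without progressive disease?** The two rows of Appendix N, with footnote 7, compare as follows.

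| Relapse criterion | Counterpart under progressive disease | Relapse without progression? |
|---|---|---|
| Hemoglobin fall above 2 g/dL | None | Yes |
| Creatinine rise of 2 mg/dL or more | None | Yes |
| 5% marrow cut-off for relapse from CR | Plasma cells above 10% | Yes, between the two cut-offs |
| Calcium above 11.5 mg/dL | Same level, but attributable only to the plasma cell disorder | Only where that attribution fails |
| New or definitely larger plasmacytomas or bone lesions | Essentially the same | No |

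**Step 4: a worked case.** Take a myeloma patient whose hemoglobin falls from 10.5 to 8.4 g/dL on two consecutive assessments while the M-protein is unchanged. The fall is 10.5 − 8.4 = 2.1 g/dL, which exceeds 2. Suppose the investigator records clinical relapse.

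- SAP 6.3 read literally: a PFS event on that date.
- Appendix N: no event. The patient stays at risk until IMWG progression or a qualifying death, or is censored.

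**Step 5: how reachable are the routes?** Hemoglobin and creatinine are measured on Day 1 of every cycle (7.2.2.5.1 and 7.2.2.5.2), so the data exist. The investigator must still document a relapse, and the relapse row describes that reporting as optional. The marrow route is narrower: Table 7-1 schedules myeloma marrow only at screening and to confirm CR, so it needs an unscheduled sample.

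**The case against.** The best defense is that the documents already resolve this. Protocol 10.5.2 ties PFS to the appropriate hematological criteria. For myeloma those are in Appendix N, which states its own PFS rule, and the SAP introduction says the data are analyzed according to Section 10 of the protocol. On that reading the specific rule governs, and relapse is a generic term serving other diseases. The censoring sentence in SAP 6.3 also speaks only of subjects without disease progression.

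This is probably what was intended, and it softens the conflict. It does not remove it. Section 10.5.2 goes on to list relapse as an event without qualification. SAP 6.3, the text to be programmed, cites no criteria or appendix, whereas SAP 6.2 does refer to disease-specific criteria for response.

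A reader might infer three stronger points that the documents do not support:

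- **Duration of response is affected in the same way.** Protocol 10.5.2 does end DOR at progression or relapse, but Appendix N restricts only time to progression and PFS. It says nothing about DOR.
- **Drug-related creatinine rises will often be counted as progression.** Table 1-1 reports increased creatinine in 15.3% at all grades, but in 0 of 255 at grade 3/4. It does not show that anyone reached a rise of 2 mg/dL.
- **The shift in the pooled curve can be calculated per patient.** The accruals in SAP Table 1 sum to 20 + 15 + 6 + 8 + 6 + 15 + 2 = 72, but that table has no myeloma group. The protocol plans 70–90 patients, and the SAP records early termination. The documents give no basis for a figure.

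**Conclusion.** The inconsistency is real and minor. As written, SAP 6.3 can assign a PFS event to a myeloma patient who does not have IMWG progressive disease, against the criteria the protocol adopts. The error runs one way: the literal rule can only bring an event forward or add one.

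The size cannot be stated. Myeloma is not among the tumor types the protocol expects or the six groups named in SAP 10.1, and neither document says that a myeloma patient enrolled. If none did, no result changes. PFS is a descriptive secondary endpoint without hypothesis testing, separate PFS analyses need a cohort of at least 10 subjects, and no success or futility decision uses it.

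The conclusion assumes that an investigator documents a relapse resting only on a criterion with no match under progressive disease, and that the analyst applies SAP 6.3 as it stands.

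**What to change.** Add to SAP 6.3:

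> For multiple myeloma, relapse, clinical relapse and relapse from CR (Appendix N) do not count as PFS events; progression is IMWG progressive disease. All other PFS rules in this section, including the 30-day limit on deaths and progression recorded as the reason for discontinuation, apply unchanged.

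The second sentence keeps myeloma patients under the same death and discontinuation rules as everyone else. Align protocol 10.5.2 using the first sentence only, because the 30-day limit and the discontinuation rule are in the SAP and not in that section. The pairing of progression with relapse in SAP 2.1 should then be read in the same sense.

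Do not delete relapse from the general definition. The AML criteria in Appendix E have no progressive disease category and rely on relapse from CR or CRi, and the ALL criteria in Appendix F also use that category.

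The cost is two sentences in the SAP and one in the protocol. No new data are needed.
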